
STATISTICAL DESIGN AND POWER

Sample Size and Power

The total proposed enrollment of 280 women was determined considering a feasible rate of recruitment, expected effect size of the AME intervention on primary outcomes, testing of multiple hypotheses, and anticipated rate of attrition and protocol non-adherence at 2 weeks postpartum (primary outcome assessment). Our recent intervention research with normal weight and overweight/obese women demonstrates medium sized effects (standardized mean difference, d) for the AME intervention at 1-2 weeks postpartum compared to an education control in terms of higher levels of breastfeeding selfefficacy (AME: M=52.59, SD=9.92, Education: M=45.71, SD=15.71, d=0.53) and greater percentage of breast milk feeds (AME: M=89.50, SD=20.372; Education M=78.64, SD=27.303, d=0.45). Regarding exclusive breastfeeding at 1-2 weeks, rates of 0.27 have been reported among overweight/obese women.32 With a sample size of at least 210 (105 per group), we can detect with .80 power betweengroup differences in the proportions in breastfeeding exclusivity at 2 weeks postpartum as small as .172 (medium effect size of OR=2.55 using likelihood ratio chi-square statistics) at an adjusted test-wise significance level of .0167. While there is a fair amount of heterogeneity in the published effect sizes for breastfeeding support interventions among overweight and obese women and for AME specifically, our estimate lies in the range of reported effect sizes in the field. 12,32 While the examination of long-term efficacy of AME is more exploratory (Aim 2), we will be able to detect small to medium interaction effects between groups over time as small as f = .323 when using repeated measures F-tests with at least four postpartum outcome time points. Our pilot work and previous studies utilizing similar populations and recruitment sites indicate that we can conservatively anticipate combined study attrition and intervention dropout at ≈25%. To ensure 210 participants with complete follow-up to 2 weeks and no protocol deviations, we will enroll 280 women.

Statistical Methods

Preliminary Analyses: For Aims 1 and 2, detailed exploratory data analyses will first be performed, involving data description and data screening for anomalies (e.g., outliers, nonnormality, etc.). The results from this initial investigation will be used to: 1) describe

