univariate and bivariate data distributions; 2) identify imbalances between treatment groups and associations between the dependent variables and suspected covariates/confounders; 3) evaluate the amount and patterns of missing data; and 4) check for violations of statistical assumptions for the planned analyses. If statistical assumptions are seriously violated, data transformations or more statistically robust methods will be considered. Covariates/confounders will be included in models secondarily, and their impact on the effect of the primary independent variable on the study outcomes will be evaluated. The randomness of missing data will be investigated using available information on subject characteristics to help discern patterns in the missing data, identify the possible covert missing data mechanisms, and inform the choice of the strategies to handle missing data. We will conduct logistic regression models to compare the characteristics of participants who remained in the study versus those who dropped out to determine if data are missing at random. If data are ignorably missing (i.e., not related to the outcome itself), likelihood estimation procedures, such as those in SAS PROC MIXED, GLIMMIX and NLMIXED as well as Mplus, will produce unbiased estimates while allowing us to retain cases with missing values on the outcome variables. If needed, multiple imputation would be used to impute missing values on the predictor variables. If data are not ignorably missing (i.e., non-randomly missing), we may use pattern mixture modeling to account for informative attrition.

Analysis Strategies for Aims 1 and 2: To examine the efficacy of the remotely-delivered AME intervention relative to the attention control on breastfeeding outcomes during hospitalization to the first two weeks postpartum (short-term; Aim 1) and up to the first 12 months (long-term; Aim 2) among overweight and obese (BMI \geq 25) women, an intent-to-treat (ITT) approach will be used, where all participants will be included in analyses as randomized, regardless of protocol adherence/deviations, treatment received, or withdrawal. Adherence to the assigned intervention, however, will be monitored, and the sensitivity of the results under the ITT model will be explored to identify the effects of the amount of intervention received (e.g., number of AME study visits) and deviations in protocol on outcomes.

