The primary outcome variables of interest for the short-term efficacy of the AME intervention at 2 weeks postpartum (Aim 1) are 1) proportion of mothers providing 100% breast milk, 2) percentage of feedings that were breast milk, and 3) breastfeeding self-efficacy. Secondary breastfeeding outcomes for short-term efficacy include proportion of mothers with any breastfeeding, perceived milk supply, onset and days to lactogenesis II, and days to any formula and/or breastfeeding cessation. Secondary long-term efficacy outcomes (Aim 2), which will be assessed at all follow-up points until 12 months postpartum (or breastfeeding cessation/loss to follow-up), are duration of breastfeeding in days and any breastfeeding at postpartum follow-ups; the continuous and categorical type versions of breastfeeding exclusivity; and the proximal intervening outcomes (i.e., mediating variables) including the repeatedly measured breastfeeding self-efficacy and perceived milk supply.

Generalized linear mixed-effects modeling with linear contrasts will be used to examine the effect of treatment assignment (AME vs. attention control) for each repeatedly assessed outcome, with treatment group assignment as the between-subjects factor, time as the within-subjects factor, and an interaction between time and treatment group. Given the level of measurement and observed data distribution of the particular dependent variable, an appropriate error structure and link function to the linear predictors will be assumed. For example, for breastfeeding exclusivity and any breast feeding, each assessed as a binary variable, a binomial error structure will be assumed and a logit link to the predictors will be applied, while for the continuous type versions of breastfeeding exclusivity and the interval-scaled breastfeeding self-efficacy, a normal error

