distribution will be considered with an identity link to the linear predictors. Random effects for participants will also be included. Fixed and/or time-dependent covariates (e.g., pre-pregnancy BMI category [25.0-29.9; 3034.9; 35-39.9; 40+]) may be included secondarily to adjust for group imbalances or variables related to the dependent variables based on the literature or data screening results. Standard fit criteria (e.g., AIC and BIC) also will be used to identify the best-fitting repeated measures covariance structure. F-tests will test the main and interaction effects included in the model. Individual regression parameters will be estimated with confidence intervals. For each model, residual analyses will be conducted to identify sources of model misspecification, outliers, and influential observations. Sensitivity analyses will be performed to discern the impact of influential cases on modeling results. Linear contrasts will be specified in the repeated measures models to test whether the AME intervention demonstrates greater improvements in breastfeeding outcomes compared to the attention control at each time point, in particular, when conducting hypothesis testing on the primary short-term outcomes. Point and interval estimates will be obtained for each of the comparisons examined.

For event history type outcomes (e.g., breastfeeding duration, days to the onset of lactogenesis II, days to any formula) Cox proportional hazards regression methods will be applied to allow for possible censoring of the event of interest and inclusion of the fixed and time-dependent predictors. For summary outcomes (e.g., proportion of breast milk in-hospital), generalized linear modeling will be applied.

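### The sizing sentence gives .172 and OR 2.55 as one detectable effect, but at the cited base of .27 they differ; secondarily, the 2-week exclusivity odds ratio is conditional by default and no marginal effect is planned beside it

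*Combined protocol and SAP*

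**What the plan says.** **Sizing (Sample Size and Power).** The base rate comes from the statement that "rates of 0.27 have been reported among overweight/obese women". With 105 women per group, power of .80 and a test-wise level of .0167, the plan says that it can detect a difference in exclusivity at 2 weeks "as small as .172 (medium effect size of OR=2.55 using likelihood ratio chi-square statistics". Allowing about 25% for attrition and dropout, it enrols 280.

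**Analysis (Statistical Methods, Analysis Strategies for Aims 1 and 2).** The first primary outcome is "1) proportion of mothers providing 100% breast milk". As a repeatedly assessed binary outcome it goes into a generalized linear mixed model, for which "a binomial error structure will be assumed and a logit link to the predictors will be applied". The section adds: "Random effects for participants will also be included". The 2-week comparison is a linear contrast in that model, and regression parameters are to have confidence intervals. On reporting, the plan says: "Point and interval estimates will be obtained for each of the comparisons examined". It does not say whether the exclusivity effect will be a risk difference or an odds ratio, nor whether it will be marginal or conditional. A model without random effects is planned only elsewhere: "For summary outcomes (e.g., proportion of breast milk in-hospital), generalized linear modeling will be applied". The preliminary step describes "univariate and bivariate data distributions", so raw arm proportions may appear there, but it plans no interval for their difference.

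**The concern.** A base rate, a difference and an odds ratio cannot all be chosen freely: any two fix the third. Here the three do not fit. A reader who relies on the .172 would take a null result as evidence against rises that the trial had only moderate power to find.

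The second matter is what the reported effect will mean. The sizing compares two proportions, so its OR is marginal. The planned contrast, once exponentiated, is an odds ratio for a given value of the participant effect. When there is an effect and the random-effect variance is above zero, this lies further from 1 than the marginal OR, whether the effect is benefit or harm. Without a label, a reader could set it beside 2.55, or beside trials that report proportions, and misjudge the effect.

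**Working it through.** **Inputs.** From Sample Size and Power: base p₁ = .27, n = 105 per group, level .0167, power .80, difference .172, OR 2.55. Allocation is 1:1 (study procedures). The plan does not state sidedness; two-sided is assumed, since it reproduces 105 per group.

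**Formulas.** Pooled normal power = Φ[(d − z·s₀)/s₁], with z = 2.393, s₀ = √(2p̄(1−p̄)/n) and s₁ = √((p₁(1−p₁)+p₂(1−p₂))/n). Likelihood ratio power = P(χ²₁(λ) > 5.73), with λ = 2n·Σ[p ln(p/p̄) + (1−p) ln((1−p)/(1−p̄))] summed over the two arms.

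**1. The plan's figure, taking OR 2.55.**
- Base odds: .27/.73 = .3699. Times 2.55 = .9432. So p₂ = .9432/1.9432 = .485, a rise of .215.
- Pooled normal: (.2154 − 2.393 × .0669)/.0652 ≈ .85, power .80. Likelihood ratio: λ = 10.47, power .80. Exact enumeration: .81.
- Enrolment: 210/(1 − .25) = 280.

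So 105 per group and 280 in total reproduce for OR 2.55.

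**2. Taking a rise of .172.**
- p₂ = .442; odds .442/.558 = .7921; OR = .7921/.3699 = 2.14.
- Pooled normal: (.172 − 2.393 × .0661)/.0650 ≈ .21, power .58. Likelihood ratio: λ = 6.83, power .59. Exact enumeration: .59.
- With all 280 analysed (140 per arm), power is .73, and the smallest rise detectable with .80 power is .185. Power of .80 for .172 needs 161 per arm.

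**3. Where .172 could come from.** A fall from .27 to .098 gives (.172 − 2.393 × .0535)/.0521 ≈ .84, power .80 (likelihood ratio .81). But its odds ratio is (.098/.902)/.3699 = .29, or 3.40 when inverted, not 2.55. The documents do not say how .172 was obtained.

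**4. Could another reading rescue the pair?** As rises, .172 and OR 2.55 agree only at a base of .168 or .660, where power is .69. A one-sided .0167 test from .27 gives .69 for .172 and .87 for OR 2.55. Neither reading gives .80 for both.

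**5. Conditional against marginal odds ratio.** Take logit P(Y=1|u) = α + β·group + u, with u normal with mean 0 and SD σ. Choose α and β so that averaging over u gives the stated arm proportions; exp(β) is then the conditional OR. Every σ here is assumed.

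| Arm proportions | Marginal OR | σ = 1 | σ = 2 | σ = 3 |
|---|---|---|---|---|
| .27 and .485 | 2.55 | 3.1 | 4.6 | 7.4 |
| .27 and .15 | .48 | .43 | .32 | .23 |
| equal | 1.00 | 1.00 | 1.00 | 1.00 |

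**6. Which interval matches the test.** A two-sided test at .0167 corresponds to a 98.33% interval. Exact enumeration with 105 per arm compared whether a Wald interval for the risk difference excludes zero with a likelihood ratio test at .0167. A 95% interval disagrees with the test in 9.9% of trials at .27 and .485, and in 15.8% at .27 and .442. A 98.33% interval disagrees in under 1% at each.

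**The case against.** **On the sizing sentence.** The plan speaks of a difference, not a rise, and .172 is very nearly the detectable fall from .27, so this may be two solutions of one calculation placed in one sentence. That is plausible, but it does not make the sentence right: the hypothesis is improvement, and the fall has a different odds ratio. It is also fair that the intention-to-treat analysis covers all randomised women, so .59 alone would be too bleak; .73 belongs beside it. A reader might go further and infer that the trial is undersized and needs 161 per group. The documents do not support that, because 105 per group is exactly what OR 2.55 requires and nothing shows that .172 was the intended target.

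**On the odds ratio.** A conditional OR is a valid estimand, nothing in the plan requires comparability with the planning OR, and confidence intervals for regression parameters under a logit link already point to the log-odds scale. All of that stands, which is why this part is secondary. What remains is that conditional or marginal is never stated. Choosing the covariance structure by fit criteria might suggest a marginal model, but participant random effects are stated without condition. A reader might infer that the published effect will be greatly exaggerated. That does not follow: the table in the working rests wholly on assumed SDs, and the gap vanishes with no effect or zero variance.

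**On missing outcomes.** A marginal summary might seem to call for imputing the week-2 outcome. This point does not require it: Preliminary Analyses already plans likelihood methods that keep women with missing outcomes, and pattern mixture models if needed.

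**Conclusion.** The sizing sentence is wrong as written. At .27, with 105 per group and two-sided .0167, the rise detectable with .80 power is about .215 (OR 2.55). A rise of .172 has power of about .59, or about .73 with all 280 analysed. This rests only on the plan's own figures and the assumption of a two-sided test, and a one-sided test does not repair it. Enrolment is not in question if OR 2.55 is the target.

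The reporting part is an improvement rather than an error. The default odds ratio is conditional and further from 1 than the marginal one when an effect exists, but by how much cannot be said from the documents. The hypothesis test is essentially unaffected, provided that the random-effect variance can be estimated.

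**What to change.** **Sample Size and Power.** Restate the detectable difference as about .215 (from .27 to .485, OR 2.55), or keep .172 and state its OR as 2.14 and its power as about .59. State the sidedness. Leave enrolment at 280. The cost is one corrected figure.

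**Analysis Strategies for Aims 1 and 2.** Add that:
- the mixed-model contrast at .0167 remains the deciding test for 2-week exclusivity;
- arm proportions, a marginal risk difference and a marginal OR will be reported beside it, by one method named in advance;
- these will carry 98.33% intervals to match the test level, with 95% intervals added as descriptive if wanted;
- the mixed-model OR will be labelled as conditional on the participant.

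Two candidate methods are averaging the fitted mixed model over its random effect, and standardising a week-2 logistic model over the randomisation BMI strata. The first needs an estimable random-effect variance; the second does not, but without further steps it uses only women with week-2 data. The cost is a short reporting paragraph and a little extra analysis. Test and interval may still occasionally disagree near the threshold, which is why the deciding test should be named.

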Recruitment of prospective participants is detailed in the recruitment section. In all cases, once contact is made with a prospective participant, study personnel will provide a brief synopsis of the study, including study purpose, study procedures, potential risks and benefits, compensation and right to withdrawal from the study at any time without penalty. If interested in participating, study personnel will administer a brief screening form to the participant to ensure eligibility criteria are met. If ineligible, the participant will be informed of the reason for ineligibility and screening information will be retained without the participant's identifiable information (name, birthdate, etc.). If eligible, the research personnel will complete informed consent with the maternal participant. This informed consent may be completed in-person on paper, or remotely with a member of the research staff via Zoom (or similar platform) with an e-signature. Maternal participants will provide permission/consent for their infants to participate in the study, as infant-specific data, including background birth information and infant measurements, will be collected and the intervention has the potential to affect infant health. In all cases, maternal participants will sign and receive a copy (either hard copy or electronic copy) of the informed consent document. Any paper original copies will be kept and filed by research personnel. A separate addendum informed consent will be obtained to video-record AME sessions for interrater reliability. After informed consent, participants will complete baseline study measures/surveys (in-person, over phone or remote video/Zoom, or emailed survey; assessing maternal/fetal health, maternal demographics, maternal mood, reproductive history, body image concerns, experiences of discrimination, etc; see questionnaires for specifics) and be randomized to a group via computer-generated permuted block randomization stratified by pre-pregnancy BMI status (overweight: 25-29.9 or obese: ≥30). Subjects will have a 1:1 chance of being randomized to either study group, as indicated in the consent document. Study participation will be documented in the maternal participant's electronic medical record to alert providers to study participation. Study staff will meet remotely or in-person with participants in both groups weekly from 37 to 40 weeks of gestation for delivery of the assigned intervention. To maximize participant convenience and safety of all involved (given new standards/recommendations around social distancing) study "visits"/contact points will have the potential to be conducted completely remotely via a secure video call (e.g., HIPAA-compliant Zoom call with screen sharing when needed), audio phone call, or emailed survey. When/if feasible, preferred, and safe according to University research standards and current county-level guidance/restrictions, visits may also involve in-person meetings between the study participant and study staff (though the experimental condition lactation consultants will always deliver the intervention remotely). In-person visits may occur at the hospital/clinics before/after a prenatal visit or another mutually agreed upon convenient, private place. The details of study visits, according to assigned intervention are detailed below. Experimental Condition (AME): With the assistance of study staff, who will facilitate all study visits, participants randomized to AME will complete a test video call at enrollment, if possible, with the telelactation provider who are available for on-demand, one-on-one visits, 24/7) to increase familiarity with the service prior to AME instruction. Note that for subsequent study visits, if for any reason an IBCLC is not available, the study may use a substitute remotely-based IBCLC who is trained in study procedures. Participants will be taught the AME technique at the 37 week study visit after first viewing an introductory video demonstrating the technique. At the visit, study staff will initiate a 3-way meeting/connection with an available, remote International Board-Certified Lactation Consultant (IBCLC) and the study participant if the visit is remote (e.g., Zoom video call). If the study visit is inperson, study staff will initiate remote 2-way connection between themselves and study participant with a remote IBCLC via a secure video platform (e.g., Zoom). After connecting, the remote IBCLC will provide video-based expert instruction and guided feedback on AME and milk collection as the participant engages in the technique. Note that IBCLCs are trained in hand-expression as a fundamental professional skill and will receive additional training and oversight by study personnel (see intervention fidelity below). For participants whose study visits are conducted completely remotely, these meetings will occur via a secure HIPAA-compliant platform like Zoom which allows study participant, study staff, and IBCLC to see/converse with each other simultaneously. This will require that participants use their own electronic device (e.g., smart phone, laptop) for the visit. These meetings will be scheduled a convenient time for the participant, IBCLC, and study staff. When a video-based remote connection is not possible or problematic (e.g., WiFi issues), study staff will initiate a 3-way audio only phone call instead with the IBCLC and participant, and hand expression education will occur over audio to the extent possible, with subsequent referral to supplementary streaming videos demonstrating hand expression. As per our pilot study protocol, AME will continue for a maximum of 10 minutes during study visits (participants will also be advised to do AME for no longer than 10 minutes during their independent practice between study sessions). For any in-person study visits, any milk output will be collected into study-provided containers and syringes and stored for future analyses as per the protocol outlined below (disposition of antenatal milk). During remote sessions, any AME milk that is collected may be labeled as milk that may be given to the study, and frozen by the participant. This milk may then be collected and aliquoted by study staff at a later date (e.g., no contact porch pick-up of milk at participant's home by study staff members). For all AME sessions, additional breastfeeding education will be provided by the IBCLC as requested by participant and documented by study staff. Study staff will facilitate the overall visit (e.g., introductions, provision of milk collection containers). IBCLCs will reinforce/provide feedback on AME technique at each weekly study visit until delivery, with a similar format to the initial visit. Around the time of the initial 37 week visit (this may be before or after the visit, dependent on mode of AME education delivery), study staff will provide participants oral and written instructions to continue AME 1-2 times/day at home until delivery. Instructions (reinforced in weekly visits) will also contain information on milk storage, transport to the hospital if participant is storing milk at home, and use; AME contraindications; and when and how to seek assistance for any problems (please see attached: brochures in "other" documents). Please note that for participants whose visits will occur remotely, members of study staff will drop off supplies for AME (e.g., collection containers, labels, syringes, refrigerator boxes for transport of milk to hospital) before the first scheduled visit, so that participants have supplies at the time of their first session. These will be done in accordance with any county standards in-place at the time (i.e., no-contact porch drop-off deliveries, PPE worn if any in-person contact). Compliance with home practice, including AME timing, milk volume obtained, and any problems, will be assessed from after the first study visit until delivery via daily web-based survey "diaries" (if participant declines web-based diaries or there are technical problems with web-based diaries, participants may be provided written diaries to be returned to study personnel at a time/place to be arranged, e.g., no contact porch pick up). Web-based survey diaries will be administered with an automated SMS notification sent daily to the participant with up to 3 reminders through the day to complete. The responses to web-based diaries will be automatically recorded in a secure Access study database; if participant completes written diaries, their answers will be manually entered in Access database by study staff. With regard to the SMS alert system for the web-based diaries, a two-way text messaging system has been built at the University and associated hospital for this purpose (as has the survey/diary system itself); the system utilizes a server

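### Randomisation is stratified by BMI class, but the mixed models behind the primary 2-week tests leave BMI as an optional secondary covariate; if BMI is prognostic, a little power goes unused.

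*Combined protocol and SAP*

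**What the plan says.** The procedures text of the combined protocol and SAP describes "computer-generated permuted block randomization stratified by pre-pregnancy BMI status (overweight: 25-29.9 or obese: ≥30"), with 1:1 allocation.

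Analysis Strategies for Aims 1 and 2 sets out the mixed model used whenever an outcome is measured at several waves: "with treatment group assignment as the between-subjects factor, time as the within-subjects factor, and an interaction between time and treatment group". It then adds: "Random effects for participants will also be included". The primary short-term hypotheses are tested inside these models: "Linear contrasts will be specified in the repeated measures models to test whether the AME intervention demonstrates greater improvements in breastfeeding outcomes", compared with the attention control at each time point.

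Pre-pregnancy BMI, in four categories, appears only as an example of covariates that "may be included secondarily to adjust for group imbalances or variables related to the dependent variables based on the literature or data screening results". The Preliminary Analyses paragraph likewise puts covariates in secondary models and evaluates their influence on the treatment effect.

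For the other model types the plan is open rather than exclusive. The Cox models allow for censoring "and inclusion of the fixed and time-dependent predictors", with no predictor listed. For summary outcomes the text says only that "generalized linear modeling will be applied".

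**The concern.** Blocks within BMI strata force the arms to have nearly the same BMI mix, so most of the between-stratum difference drops out of the treatment contrast. A model without the stratum still counts that difference as residual variance. The estimated standard error is then larger than the true one, and a test at .0167 rejects less often than it should.

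The conditions under which BMI may be added do not settle this. Stratification is meant to prevent BMI imbalance, so that trigger is the least likely to operate. The other triggers, literature and data screening, leave the choice open until data have been examined. The named covariate also has four levels, and the two-level stratum is never listed as a model term.

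What is at stake is power in the primary 2-week tests, not validity.

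**Working it through.** **Inputs from Sample Size and Power.** 280 enrolled, 25% combined loss, 210 analysed (105 per group), test-wise alpha .0167, d=.45 (percentage of breast milk feeds), d=.53 (self-efficacy), control rate .27 and OR 2.55 (exclusivity). I take the tests as two-sided, which reproduces the plan's power.

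**Assumptions.** The documents give no outcomes by BMI class. I assume gaps of .2, .5 and .8 SD between strata, strata split about 50/50, blocks of 4, and the whole 25% missing at random at 2 weeks.

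**The plan's own figures.** .05/3 = .0167 and 210/(1 − .25) = 280. OR 2.55 from .27 gives .485; with 105 per group, power is .800 by the likelihood-ratio test. (That difference is .485 − .27 = .215, not the stated .172. I use the OR here; the mismatch is a separate matter.)

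**What the assumed gaps mean.**
- Breast milk feeds: pooled SD = √((20.372² + 27.303²)/2) = 24.09. The gaps are 4.8 / 12.0 / 19.3 points, against an expected effect of 89.50 − 78.64 = 10.86.
- Self-efficacy: pooled SD = √((9.92² + 15.71²)/2) = 13.14. The gaps are 2.6 / 6.6 / 10.5 points, against an expected effect of 52.59 − 45.71 = 6.88.

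So .5 SD is about as large as the treatment effect itself, and .8 SD is extreme.

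**Continuous outcomes, one time point.** With within-stratum variance 1 and a 50/50 split, the stratum adds k = .25 × gap² = .01 / .0625 / .16.
- Estimated SE, unadjusted over adjusted: √(1+k) = 1.005 / 1.031 / 1.077.
- After 25% loss about a quarter of the between-stratum variance returns to the contrast. True over estimated variance of the unadjusted contrast is (1+.25k)/(1+k) = .993 / .956 / .897.
- Actual alpha: dividing z = 2.393 by the square root of that ratio gives .0163 / .0144 / .0115. With perfectly balanced strata it is .0162 / .0136 / .0099.
- Power at d=.45, with m = .45/√(2/105) = 3.261: unadjusted Φ((m − z)/√ratio) = .808 / .812 / .820; adjusted Φ(m√(1+k) − z) = .812 / .833 / .868. The gain is 0.4 / 2.1 / 4.8 points.

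Simulating the randomisation and loss (200,000 null runs done twice, 100,000 power runs) agrees:

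| Gap (SD) | Unadjusted alpha (two runs) | Power d=.45, unadjusted vs adjusted | Gain d=.45 | Gain d=.53 |
|---|---|---|---|---|
| .2 | .0165, .0162 | .800 vs .804 | 0.3 | 0.1 |
| .5 | .0146, .0141 | .808 vs .828 | 2.0 | 1.1 |
| .8 | .0114, .0115 | .812 vs .861 | 4.8 | 2.4 |

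Gains are in points, from unrounded power. With no gap the unadjusted alpha is .0171 and .0170. An assumed 35/65 split gives gains of 0.3 / 1.9 / 4.6 points at d=.45.

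**Exclusivity.** Single-time-point logistic likelihood-ratio test, .27 versus .485, assumed stratum ORs 1.5 / 2.06 / 4.1 (the last extreme):
- Power, unadjusted vs adjusted: .806 vs .810, .809 vs .821, .814 vs .851.
- Unadjusted alpha .0170 / .0159 / .0137 (.0176 with no stratum effect); adjusted .0171-.0179.

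**Repeated measures.** Five waves (2, 6 and 12 weeks, 6 and 12 months), within-person correlation .5 (assumed), complete data, gap .5 SD at 2 weeks. The table gives the SE of the 2-week contrast relative to the model with stratum and stratum-by-time.

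| BMI effect over time | Covariance | No stratum | Stratum main effect only |
|---|---|---|---|
| Constant | either | 1.031 | 1.000 |
| Fades evenly by visit to 0 at 12 months | unstructured | 1.031 | 1.008 |
| Same | random intercept | 1.012 | 1.004 |
| Present at 2 weeks only | unstructured | 1.031 | 1.020 |
| Same | random intercept | 1.006 | 1.005 |

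The random-intercept rows average the added variance over the waves. For fading by visit: .0625 × (1 + .5625 + .25 + .0625 + 0)/5 = .0234, and √1.0234 = 1.012. Fading by calendar time gives 1.017. The covariance is chosen from the data ("Standard fit criteria (e.g., AIC and BIC) also will be used to identify the best-fitting repeated measures covariance structure"), so which row applies is not known in advance.

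**The case against.** The strongest reply is that no stated inference is harmed. The planned contrast is valid, errs on the safe side and still reaches about .80 power at the planned effects. The plan names BMI as its example covariate, with a category boundary at 30 that nests the stratum, so a BMI-adjusted result is foreseen. Only its rank as secondary and the word may are in dispute. All of this stands, and it is why the point is minor.

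It also stands that nothing in the documents shows BMI class to be prognostic within this population, and that the larger gains come from large or extreme gaps. The single-time-point figures can overstate the loss: under a random-intercept covariance with a fading BMI effect, the 3.1% SE excess at a .5 SD gap falls to between 0.6% and 1.7%. No binary mixed model was run, so the exclusivity gains are only indicative, and part of them reflects the adjusted test's slightly higher actual alpha.

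Adding the stratum to a logit model also makes the odds ratio conditional on BMI class: 2.55 becomes about 2.59 to 2.71 if control rates differ by 10 to 20 points. The planned model is already conditional on participant through its random effects, so one sentence on the estimand deals with this.

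None of these points gives a reason to leave the stratum out of the main model.

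**Conclusion.** The concern holds, as a minor point of efficiency. The omission is shown for the mixed models only; in the Cox and summary models the stratum is merely not named. If BMI class is prognostic, the continuous primary tests run at about .016 (gap .2 SD), .014-.015 (.5 SD) or .011-.012 (.8 SD) instead of .0167, under the stated assumptions on split, block size and random loss. For exclusivity, alpha is practically nominal unless the stratum effect is extreme. At a modest gap the power cost is a fraction of a point; at a large one it is about two points, or less if the BMI effect fades and a random-intercept covariance is chosen. Confidence is high that the plan does not commit to the stratum, whereas the actual loss cannot be known from the documents.

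**What to change.** In Analysis Strategies for Aims 1 and 2, prespecify the two-level randomisation stratum (25-29.9 versus 30 or more) as a fixed effect in the main mixed models, together with stratum-by-time. The interaction is needed because a main effect alone recovers the full gain only if the BMI effect is constant over follow-up. The four-level BMI category would also serve if fixed in advance, again with its interaction with time. State that the exclusivity odds ratio is conditional on the stratum.

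For consistency, name the stratum as a predictor in the summary models and stratify the Cox models by it. Keep other covariate-adjusted models secondary, using baseline covariates fixed before outcomes are seen by arm.

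The cost is SAP wording and two terms in the mixed models. No new data are needed.
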